### **8.1.18. Blood Biomarkers of Inflammation**

Blood to assess biomarkers of inflammation will be collected at Baseline and post-treatment in all subjects. The messenger ribonucleic acid (mRNA) levels of key cytokines and chemokines in DM will be analyzed. The exact biomarkers to be analyzed will be decided after completion of the study, but may include Type 1 IFN, IL-1 $\beta$ , IFN $\beta$ , IL-6, IFN $\gamma$ , and TNF $\alpha$ , and results may be reported separately from the main CSR.

### **8.1.19. Paxgene**

Blood will be collected for transcriptomic analysis, at Baseline and post-treatment in all subjects. Results of such analysis may be reported separately from the main CSR.

### **8.1.20. Blood for Flow Cytometry**

Blood will be collected for flow cytometry at selected sites. It is expected that all subjects at these subsites will provide a blood sample for flow cytometry at the visits specified in the SOA.

### **8.1.21. Autoantibodies**

Blood will be collected to assess autoantibodies commonly seen in DM patients, at Baseline and post-treatment in all subjects. Results of such analysis may be reported separately from the main CSR.

### **8.1.22. Skin Biopsies**

Skin biopsies (at Baseline, Visit 4, and at and at the end of treatment [Visit 10 or Early Termination]) will be collected in consenting subjects at selected sites. Five 4mm skin biopsies will be collected (other than site 1001) 2 each at Visit 1 and Visit 4 respectively for histology and transcriptome and 1 at Visit 10 for transcriptome. The biopsies will preferentially be taken from an area of involved skin that is active or worsening, rather than improving, in the opinion of the site investigator. No biopsies will be taken from the face, neck, hands or feet. Biopsies should be taken from the same location at each biopsy visit, provided that this area is active or worsening at that timepoint. If a subject has no active skin involvement in an area that can be biopsied at Visit 1, then no biopsies should be taken at Visit 1 or any subsequent visit (because there will be no Baseline biopsy for comparison). If biopsies are obtained at Visit 1, then subsequent biopsies should be obtained within 1-2 cm of the first biopsy sites, without regard to disease activity at that site at that time.

Histology will be evaluated by a blinded pathologist post-treatment and compared to Baseline. Flow cytometry may be conducted to analyze cell subsets in the skin and transcriptome analysis may be performed to assess RNA levels. Skin biopsy results may be reported separately from the main CSR.

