v Five optional, 4 mm skin biopsies will be collected: two at Visit 1, two at Visit 4 and one at Visit 10. At Site 1001, subjects will have the option to consent to two 6 mm and three 4 mm biopsies (e.g., one 4 mm and one 6 mm at Visit 1; one 4 mm and one 6 mm at Visit 4, and one 4 mm at Visit 10). Skin biopsies will only be conducted at selected sites.

w Subjects who rollover into Part B should sign an ICF by Visit 10 and preferably earlier than Visit 10, if possible.

x The Safety Follow-up Visit is to occur  $4 \pm 1$  weeks after the last visit (V10/ET) and is to be completed by subjects who do not rollover into Part B.

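### Section 8.1.22 gives two conflicting rules for follow-up skin biopsies, and one of them selects the tissue on post-treatment disease activity

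*Protocol*

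**What the plan says.** Three sentences in Protocol Section 8.1.22 bear on where tissue is taken.

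- A general preference, not tied to a visit: "The biopsies will preferentially be taken from an area of involved skin that is active or worsening, rather than improving", as judged by the site investigator.
- A same-location rule with a condition: "Biopsies should be taken from the same location at each biopsy visit, provided that this area is active or worsening at that timepoint".
- A closing rule for subjects biopsied at Visit 1: "subsequent biopsies should be obtained within 1-2 cm of the first biopsy sites, without regard to disease activity at that site at that time".

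Between the second and third stands a rule that a subject without suitable active skin at Visit 1 is not biopsied then or later, because there would be no Baseline sample to compare with.

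On use, the section says "Histology will be evaluated by a blinded pathologist post-treatment and compared to Baseline", and it mentions transcriptome analysis and possible flow cytometry. It assigns the Visit 1 and Visit 4 samples to histology and transcriptome and the single Visit 10 sample to transcriptome only. The biopsy footnote to Table 3 gives the schedule: "Five optional, 4 mm skin biopsies will be collected: two at Visit 1, two at Visit 4 and one at Visit 10". Reporting is left open: "Skin biopsy results may be reported separately from the main CSR".

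**The concern.** The same-location rule and the closing rule give opposite answers in the case that matters most for a treatment trial: the Visit 1 area has improved by Visit 4 or Visit 10. Under the first, the condition for returning to that area is not met. Under the second, the site returns to it anyway.

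This matters beyond tidiness because the first rule makes the follow-up sample depend on disease activity after treatment has begun. A before-and-after comparison on tissue chosen in that way leaves out the tissue that improved. If one arm improves more than another, more is left out there. A blinded reading of the slides does not help, since the selection happens before there is a slide, and no later analysis can recover tissue that was never taken. If sites resolve the conflict differently, the data set would also mix selected and unselected samples.

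**Working it through.** **Do the two rules really conflict?** The protocol states no figure on this point, so the first check is to set the rules side by side.

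| State of the Visit 1 area at follow-up | Same-location rule | Closing rule |
|---|---|---|
| Still active or worsening | Sample the same location | Sample near the Visit 1 site |
| Improved or cleared | Condition fails: skip, or go elsewhere (not stated) | Sample near the Visit 1 site |

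The rules agree in the first row and conflict in the second.

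**Does other text reconcile them?**

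- The same-location rule cannot be confined to Visit 1. It speaks of each biopsy visit and of activity at the visit in question, which only has meaning at follow-up.
- The sentence about subjects without active skin at Visit 1 covers only people who are never biopsied.
- The Table 3 footnote gives numbers and sizes of biopsies and no activity condition.

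So the conflict stands.

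**What happens to improved tissue under the same-location rule?** The rule does not say what to do when the condition fails. If the biopsy is skipped, the improved area contributes no follow-up sample. If it is moved to another active area, which the general preference suggests, a sample exists but comes from active skin. On both readings, improved skin at the Baseline site is not sampled.

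**Direction of the effect, by illustration.** All inputs here are assumed, none comes from the protocol, and the model covers the skipped-biopsy reading only.

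- Baseline activity B has mean 10 and SD 2.
- Follow-up is F = B − d + e, with mean fall d = 1 on placebo and d = 4 on active drug (true difference −3.0), and e normal with SD s = 3 or 4.
- The follow-up sample is kept only if F is above a cut-off c = 4 or 6.

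Let t = √(4 + s²) and a = (c − (10 − d))/t. The share kept is 1 − Φ(a). The mean change among those kept is −d + (s²/t) × φ(a)/(1 − Φ(a)).

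Worked case, s = 4 and c = 6: t = √20 = 4.472 and s²/t = 3.578.

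- Active: a = 0, share kept 0.50, ratio 0.798, mean change −4 + 3.578 × 0.798 = −1.15.
- Placebo: a = −3/4.472 = −0.671, share kept 0.75, ratio 0.425, mean change −1 + 3.578 × 0.425 = 0.52.
- Difference: −1.15 − 0.52 = −1.67, against a true −3.0.

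| s | c | Kept, placebo | Kept, active | Mean change, placebo | Mean change, active | Difference |
|---|---|---|---|---|---|---|
| 3 | 4 | 0.92 | 0.71 | −0.58 | −2.80 | −2.22 |
| 3 | 6 | 0.80 | 0.50 | −0.12 | −2.01 | −1.89 |
| 4 | 4 | 0.87 | 0.67 | −0.12 | −2.08 | −1.96 |
| 4 | 6 | 0.75 | 0.50 | 0.52 | −1.15 | −1.67 |

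A simulation with 1,000,000 subjects per arm gave the same results to within 0.01. Under the closing rule nothing is selected and the difference stays at −3.0.

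**The case against.** The best case for the plan has four parts.

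1. **The closing rule may be taken to govern.** It is the more specific sentence, it deals directly with biopsies after Visit 1, and it expressly sets activity aside. The footnote's schedule carries no activity condition either. This stands in part: a careful site could settle on the closing rule, so the text supports saying that sites may differ and not that they will. It does not remove the conflicting sentence.

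2. **The condition attaches to the location, not to whether a biopsy is done.** A reader might infer that samples from improved subjects are simply lost. The text does not say so; moving to another active area is at least as natural a reading, and then no sample is lost. This stands, and the shares kept in the table should not be read as expected losses. Improved skin at the Baseline site is still missed.

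3. **The effect is easily overstated.** A reader might conclude that a real difference would vanish, or that the results could not be interpreted. A difference in the share of resolved sites does fall to zero if resolved sites are excluded, but that is true by definition, and the protocol names no such outcome for biopsies. For a continuous measure the illustration shows attenuation, not disappearance.

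4. **The intended use is only partly visible.** The section states a comparison with Baseline, not a test between arms, and the tertiary objectives are redacted. This stands. The selection affects the comparison with Baseline in any case; the between-arm consequence applies only if the arms are compared.

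**Conclusion.** The contradiction is explicit, sits within one paragraph, and is not a product of redaction or of matters left to the SAP. The same-location rule selects follow-up tissue on post-treatment activity, so any improvement from Baseline would tend to be attenuated. The documents do not allow the amount to be computed; the illustrative range of 1.7 to 2.2 out of 3.0 rests wholly on assumed values and on the biopsy being skipped.

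The consequence is limited. The biopsies are optional, confined to selected sites, and may be reported outside the main study report. Histology is affected at Visit 4 only, and the transcriptome at Visit 4 and Visit 10. No primary or listed secondary endpoint depends on them. This is a worthwhile correction of wording, not a threat to the trial's main conclusions.

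**What to change.** Reconcile Section 8.1.22 into one sampling rule:

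- In the same-location sentence, delete the condition, that is, everything from the word provided to the end.
- Limit the preference for active or worsening skin to the choice of the Visit 1 site.
- Keep the closing rule as it stands, so that follow-up samples come from close to the Visit 1 sites whatever the activity there.

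This makes the location of the follow-up sample independent of post-baseline activity, and it matches Section 8.1.23, where end-of-treatment photographs of the same areas do not depend on activity. The cost is a small wording change in one paragraph and a note to the selected sites. It adds no biopsies to those already scheduled for consenting subjects. If some follow-up biopsies have already been taken, record whether each came from the Visit 1 area, so that relocated and skipped samples can be identified.

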### **8.1.23. Skin Photographs**

Skin photographs will be collected in consenting subjects at selected study sites. An instruction manual, detailing standardized procedures for taking skin photographs will be provided. Photographs will be taken of pre-specified body areas and any area with the most severe skin activity if that area is not included in the pre-specified body areas. Photographs of these areas

will be taken at Baseline (Visit 1) and at end of treatment (Visit 10 or ET), regardless of activity. The photos should have all identifiers removed to protect the identity and privacy of subjects and subjects should be referred to by SID only. Skin photography results may be reported separately from the main CSR.

#### **8.1.24. Pharmacokinetic Assessments**

Lenabasum and metabolite plasma concentration will be measured at Visits 1, 2, 4, 6, and 10. At Visit 1, blood will be drawn pre-dose and then  $3 \pm 0.5$  hours post-dose at the approximate time of the anticipated  $t_{max}$ . At Visits 2, 4, 6, and 10, blood will be drawn pre-dose to assess trough concentration levels. To obtain trough concentrations of lenabasum on Visit 2, 4, 6, and 10, the blood sample for lenabasum plasma concentration should be obtained between 8 and 16 hours after the last dose of study product.

### **8.2. Safety Assessments**

#### **8.2.1. Medical History and Use of Contraception**

Medical history will include subject demographics, history of DM and current treatment for DM. The medical history also will include concurrent illnesses, other current medications, past relevant medical history, smoking history (classified as one of the following: current smoker, ever smoker (defined as  $\geq 1$  cigarette per day for  $> 1$  year), or never smoker), child-bearing potential, last menstrual period (LMP) for women, and review of systems. Date of LMP and method of contraception will be assessed at screening and all visits in WOCBP.

Acceptable contraceptive methods (as stated in [Appendix 1](#)), may not be available or approved in all countries; thus, the Sponsor does not restrict respective countries from excluding unavailable contraceptive methods in the ICF.

#### **8.2.2. Concomitant Medications**

A list of current prescription and over-the-counter medications and supplements will be obtained. Concomitant medications and supplements will be recorded on the concomitant medication eCRF at screening and all visits. The medication or supplement, dose, frequency, route, start date, stop date and indication will be captured.

#### **8.2.3. Physical Examinations**

A full physical examination will include at a minimum assessments of alertness and orientation, general appearance, skin, head, eyes, ears, nose, and throat, lungs, heart, abdomen, musculoskeletal examination, and lymph nodes. Breast and genitourinary examinations are not required.

A brief physical examination will include at a minimum assessments of skin, lung, heart, abdomen, and any other area as indicated by changes in medical history.

Medically significant changes that reflect worsening from Visit 1 physical examination will be considered AEs and recorded as such.

#### **8.2.4. Vital Signs, Height and Weight**

Vital signs measurements include blood pressure, pulse rate, respiratory rate, and temperature and are assessed at Screening and all study visits. Systolic and diastolic BP will be measured with the subject supine for at least 5 minutes. The same arm should be used for the measurement throughout the study as much as possible. Pulse and respiration will also be measured with the subject supine for at least 5 minutes. Body temperature will be measured on the skin or in the mouth.

Height will be measured in standing position with footwear removed and weight will be measured with coats, jackets, and footwear removed.

#### **8.2.5. Electrocardiograms**

Twelve-lead ECGs are to be recorded with the subject in a rested supine position for  $\geq 10$  minutes before the test, using ECG machines supplied by the Sponsor. The ECGs will be read centrally. The medical significance of any new ECG abnormality will be assessed by the investigator.

#### **8.2.6. Clinical Safety Laboratory Assessments**

Blood and urine laboratory safety tests will be performed at each visit with the frequency of measures varying between laboratory parameter (sampling visits detailed below). The results of all tests will be reviewed by the investigator or designee, who will make judgments on the medical significance of any new or worsening abnormal value. New medically significant abnormal laboratory results that are related to safety of study product should be repeated as soon as possible to confirm the abnormality. The Schedules of Assessments are provided in [Table 3 \(Part A\)](#) and [Table 4 \(Part B\)](#).

The results of clinical laboratory tests at the time of last measurement before study product administration on Visit 1 will provide Baseline references against which any fluctuations in these indices can be compared.

All blood laboratory tests will be performed in a licensed, central clinical laboratory, to provide appropriate longitudinal and cross-site comparisons. The following Screening blood tests will be performed by a central laboratory:

- Complete blood count with differential
- Human immunodeficiency virus
  - At Screening, a HIV 1/2 antibody test will be performed. If the results are not negative, a HIV 1/2 antibody confirmatory test will be performed.
- Follicle stimulating hormone and leutinizing hormone
- Hepatitis B and C
  - At Screening, a test for Hepatitis B surface antigen will be performed. If the results are positive, a Hepatitis B core antibody confirmatory test will be performed.

- At Screening, a test for Hepatitis C antibody will be performed. If the results are reactive, a Hepatitis C RNA confirmatory test will be performed.
- Serum  $\beta$  human chorionic gonadotropin, for WOCBP
- Metabolic panel including glucose, urea nitrogen, creatinine, estimated glomerular filtration rate, blood urea nitrogen/creatinine, sodium, potassium, chloride, carbon dioxide, calcium, protein total, albumin, bilirubin total, alkaline phosphatase, ALT, AST, LDH, CK, Aldolase.

If retesting is required as part of Screening, any repeat laboratory screening tests will be done at the central laboratory. If returning to the clinic for repeat screening laboratory tests would cause major inconvenience for the subject, for example because of long distance travel, repeat laboratory tests can be done at a local laboratory only if results are made available to the investigator for review before dosing.

The following urine tests will be performed locally using supplies provided by the Central laboratory:

- Urine  $\beta$  human chorionic gonadotropin, for WOCBP
- Urine dipstick for blood, protein, and glucose.

Since this clinical trial is conducted globally, the same lab test kits are used in all countries in order to test under the same conditions at each site. For this reason, several kits that are not yet approved by regulatory/governmental agencies (such as MHLW in Japan) will be used (e.g., punch for skin biopsy and blood collection tube). However, these kits have almost the same structure and use as kits currently used in Japan and other countries.

## **8.2.7. Adverse Events and Serious Adverse Events**

### **8.2.7.1. Definition of Adverse Events (AE)**

An AE is any untoward medical occurrence associated with the use of a drug in humans, whether or not considered drug related (Code of Federal Regulations Title 21, Volume 5, Section 312). Another definition of an AE is any untoward medical occurrence in a patient or clinical trial subject administered a medicinal product and which does not necessarily have a causal relationship with this treatment (Article 2(m) of Directive 2001/20/EC).

An AE can therefore be any unfavorable and unintended sign (including an abnormal laboratory finding, for example), symptom, or disease temporally associated with the use of the study product, whether or not considered related to the study product. Intercurrent illnesses or injuries will be regarded as AEs. Any event of abuse, misuse or addiction should be reported as an AE. Drug abuse is defined as the intentional, non-therapeutic use of a drug product or substance, even once, to achieve a desired psychological or physiological effect. Drug misuse is defined as the use of a substance for a purpose not consistent with legal or medical guidelines (World Health Organization, 2006). Addiction (according to American Psychiatric Association) is a complex condition, a brain disease that is manifested by compulsive substance use despite harmful consequence (World Health Organization, 2006).

When collecting AEs, the recording of diagnoses is preferred (when possible) to recording a list of signs and symptoms. However, if a diagnosis is known and there are other signs or symptoms that are not generally part of the diagnosis, the diagnosis and each sign or symptom will be recorded separately. This definition also includes accidental injuries, reasons for any change in medication (drug and/or dose) other than planned titration, reasons for admission to a hospital or reasons for surgical procedures.

Abnormal results of any laboratory test or diagnostic procedure will be considered AEs if the event has any of the following characteristics:

- Results in study withdrawal
- Is associated with an SAE
- Is associated with clinical signs or symptoms
- Leads to additional treatment or to further diagnostic tests (beyond single repeat)
- Is considered by the investigator to be of clinical significance

Wherever possible the investigator should report the clinical rather than laboratory term (e.g., anaemia versus low haemoglobin value).

The investigator will assess all abnormal laboratory results for their clinical significance. If any abnormal laboratory result is considered clinically significant, the investigator must provide details about the action taken with respect to the study product and about the subject's outcome.

AEs will be captured from time of signing of IC to the end of the subject's participation in the study.

Death is not considered an AE, but the cause of death is. An exception is the event of sudden death of unknown cause. Similarly, hospitalizations and procedures are not AEs; however, the reasons for hospitalization and procedures are. However, if deemed necessary by the investigator, a procedure can be captured as an AE, along with the reason for conducting the procedure. An overdose or medication error is not an AE unless it is temporally associated with an unfavorable or unintended sign or symptom.

The investigator or designee will report all directly observed AEs and all AEs spontaneously reported by the trial subject using concise medical terminology. In addition, each trial subject will be questioned about AEs.

All adverse clinical experiences, whether observed by the investigator or reported by the subject, must be recorded, with details about the duration and intensity of each episode, the action taken with respect to the study product, and the subject's outcome.

#### **8.2.7.2. Definition of Serious Adverse Events (SAE)**

Serious AEs are a subset of AEs. A serious adverse event (SAE) is defined as any untoward medical occurrence that has any of the following outcomes:

- Results in death
- Is life-threatening

The term "life-threatening" in the definition of "serious" refers to an event in which the subject was at risk of death at the time of the event; it does not refer to an event which hypothetically might have caused death if it were more severe.

- Requires inpatient hospitalization or prolongation of existing hospitalization
- Results in persistent or significant disability/incapacity
- Is a congenital anomaly or birth defect in the offspring of a subject
- Is an important medical event

Medical judgment should be exercised in deciding whether expedited reporting is appropriate in situations where none of the outcomes listed above occurred. Important medical events that may not be immediately life-threatening or result in death or hospitalization but may jeopardize the subject or may require intervention to prevent one of the other outcomes listed in the definition above should also usually be considered serious. Examples of such events include allergic bronchospasm requiring intensive treatment in an emergency room or at home, blood dyscrasias or convulsions that do not result in inpatient hospitalization, or the development of drug dependency or drug abuse. A new diagnosis of cancer during treatment should be considered as medically important.

An AE caused by an overdose or medication error is considered serious if a criterion listed in the definition above is fulfilled. Serious AEs also include any other event that the investigator or the Medical Monitor judges to be serious or which is defined as serious by regulatory authorities.

